5.2.2 Research flowchart

5.2.3 Blood collection process table

grouping								
	Screening period							
healthy person	D-7—D0							
Cancer patients are receiving systemic treatment		Chemotherapy cycle						
		C1D1	C2	C3	C4	C5	C6	
	D-7—D0			D1± 3		D1±3		
Cancer patients who receive radical chemoradiotherapy/radiotherapy	D-7—D0	After the completion of radiotherapy/chemoradiotherapy		Four to six weeks after the completion of radiotherapy/chemoradiotherapy				
		D _{end} D _{end} +3		On the day of follow-up				
A tumor patient undergoing surgery	D-7—D0	postoperation	Postoperative discharge day/the day before discharge					
	D1—D3							

5.3 statistic analysis

This study adopted a mismatched case-control study (500 cases in the case group and 500 cases in the healthy control group). The sample size was determined based on the effect size of the previous pre-experiment (Cohen's $d=1.2$) and considering a 10% dropout rate. All statistical analyses were performed using R, with a test level of $\alpha=0.05$. Main analysis 1) Comparison of histone succinylation levels between groups - After Shapiro-Wilk normality and Levene homogeneity of variance tests, independent sample t-tests (conforming to normal distribution) or Mann-Whitney U tests (non-normal data) were selected. Report mean difference (MD)/median difference and 95% confidence interval (CI), Cohen's d effect size; 2) Diagnostic

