efficacy evaluation - Calculate the area under the curve (AUC) and its Bootstrap 95% CI through the ROC curve, and determine the optimal cut-off value by maximizing the Youden index. And calculate the sensitivity, specificity, positive predictive value (PPV), negative predictive value (NPV), and their exact Clopper-Pearson 95% CI. Secondary analysis: 1) Subgroup correlation - One-way analysis of variance (ANOVA) or Kruskal-Wallis test was used to compare the level differences among different tumor types (Bonferroni-adjusted post hoc test), and Cuzick's trend test was used to analyze the ordered association of TNM stages; 2) Therapeutic effect evaluation - The level changes before and after treatment were evaluated using paired t-test /Wilcoxon signed-rank test; 3) Prognostic value - The baseline succinylation level (median grouping) was included in the Cox proportional hazards model. After adjusting for age, stage, and treatment regimen, the hazard ratio (HR) and 95% confidence interval (CI) were calculated. The survival curve was plotted using the Kaplan-Meier method (Log-rank test). Multivariate analysis: A Logistic regression model was constructed (including succinylation level and covariates such as age and gender). AUC was compared by DeLong test, goodness-of-fit was evaluated by Hosmer-Lemeshow calibration curve, and clinical net benefit was analyzed by decision curve (DCA). If multi-site modifications are detected, LASSO regression is used to screen biomarker combinations. Quality control: Grubbs test /Winsorize for outliers, multiple imputation (MICE) for filling <5% of missing covariates. Sensitivity analysis: Robustness was verified by excluding stage I tumors, and the 70%-30% dataset was split for cutoff value training - validation. All multiple comparisons were controlled for the false discovery rate (FDR) using the Benjamini-Hochberg method.

六、Ethical requirements

Clinical research will comply with relevant regulations such as the Declaration of Helsinki of the World Medical Congress. The research can only be implemented after it has been approved by the ethics committee before it commences.

Before each subject is enrolled in this study, the researcher is responsible for providing the subject or their agent with a complete and comprehensive introduction

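### The outlier rule names Grubbs' test and Winsorizing without requiring an assay fault, for a marker the plan expects may be non-normal; if applied to a skewed marker it usually raises Cohen's d and can modestly shift sensitivity and specificity.

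*Protocol*

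**What the plan says.** All of this stands in Protocol section 5.3.

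- **Outlier rule:** "Grubbs test /Winsorize for outliers", which in its full sentence reads "Quality control: Grubbs test /Winsorize for outliers, multiple imputation (MICE) for filling <5% of missing covariates". The limit to covariates is attached to the imputation; the outlier rule carries no such limit. An assay fault, a repeat measurement or blinding to group is not mentioned.
- **Group comparison:** after normality and variance checks, "independent sample t-tests (conforming to normal distribution) or Mann-Whitney U tests (non-normal data) were selected". The plan therefore allows for a non-normal marker.
- **Effect measures:** "Report mean difference (MD)/median difference and 95% confidence interval (CI), Cohen's d effect size".
- **Accuracy measures:** the plan will "determine the optimal cut-off value by maximizing the Youden index" and then "calculate the sensitivity, specificity, positive predictive value (PPV), negative predictive value (NPV), and their exact Clopper-Pearson 95% CI".
- **Size:** "500 cases in the case group and 500 cases in the healthy control group".
- **Listed sensitivity analyses:** one leaves out stage I tumours, the other is a 70/30 split for the cut-off. Neither concerns outlier handling.

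**The concern.** The group comparison adapts when the marker is not normal; the outlier rule does not. Grubbs' test measures how far the most extreme value lies from the mean in SD units and judges that distance against a normal tail. In a right-skewed sample, valid values in the long tail fail this test in numbers that grow with the skew.

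Two sets of main results are exposed. Cohen's d has the SD in its denominator, so trimming or capping a tail shrinks the denominator. Sensitivity and specificity are exposed if values are deleted: a high control is a false positive and a high case is a true positive, and both leave the count. Rank tests are little affected, but these outputs are not rank tests. As no listed analysis keeps every value, a reader of the results could not see how much the handling contributed.

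**Working it through.** **Inputs.** From section 5.3: 500 per group, d = 1.2, Youden cut-off, Grubbs or Winsorizing. Assumed, because the protocol does not give them: marker distribution (normal, or lognormal with log SD 0.5, 0.8 or 1.0 and a case shift of 1.2 log SDs), Grubbs alpha 0.05 two-sided, one or repeated passes, by group or pooled, Winsorizing at the 5th and 95th percentiles. The plan states no figure for outlier handling, so there is none to reproduce.

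**Step 1: how many valid values does Grubbs flag?** The critical value is G = ((n−1)/√n) × √(t²/(n−2+t²)), with t the upper 0.05/(2n) point on n−2 degrees of freedom. For n = 500, t = 3.92 and G = 3.86.

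- Normal marker: 500 × 2 × Φ(−3.86) = 0.06 values expected beyond the limit. Grubbs does almost nothing.
- Lognormal, log SD 0.5: mean = exp(0.125) = 1.133 and SD = 1.133 × √(exp(0.25)−1) = 0.604. The upper limit is 1.133 + 3.86 × 0.604 = 3.47, which is 1.243/0.5 = 2.49 SDs on the log scale. Expected beyond it: 500 × 0.0065 = 3.2 valid values. Each removal lowers the SD, so repeated passes take about 5 per group in simulation.

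**Step 2: Cohen's d.**

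- Lognormal, log SD 0.5, no handling: the case/control ratio is exp(0.6) = 1.822, so d = (0.822 × 1.133)/(0.604 × √((1+1.822²)/2)) = 0.932/0.888 = 1.05.
- Normal marker, 5% Winsorizing by group: variance = 0.1 × 1.645² + 0.9 − 2 × 1.645 × 0.103 = 0.831, SD = 0.912, so d = 1.2/0.912 = 1.32. The rise needs no skew.

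**Step 3: simulation at the Youden cut-off** (lognormal, log SD 0.5, 100 replicates):

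| Handling | d | Sensitivity | Specificity | Removed, cases / controls |
|---|---|---|---|---|
| None | 1.05 | 0.734 | 0.736 | 0 / 0 |
| Grubbs repeated, by group | 1.15 | 0.729 | 0.745 | 4.9 / 4.6 |
| Grubbs one pass, by group | 1.09 | 0.733 | 0.738 | 1.0 / 1.0 |
| Grubbs repeated, pooled | 1.10 | 0.729 | 0.736 | 9.3 / 0.3 |
| Grubbs on log scale, by group | 1.06 | 0.733 | 0.736 | 0.1 / 0.1 |
| Winsorized 5%, by group | 1.23 | 0.734 | 0.736 | 0 / 0 |
| Winsorized 5%, pooled | 1.16 | 0.734 | 0.736 | 0 / 0 |

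Other runs of this scenario gave 1.22 for by-group Winsorizing, and for repeated by-group Grubbs a specificity of 0.732 to 0.745 with sensitivity 0.733 to 0.725.

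A hand check of the deletion effect with the cut-off held: 0.736 × 500 = 368 controls are below it. Removing 4.57 controls, all above it, gives 368/495.43 = 0.743. Re-choosing the cut-off adds the rest.

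**Step 4: other scenarios.**

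- Log SD 0.8 (300 replicates): specificity 0.728 with no handling, 0.750 with repeated by-group Grubbs, 0.730 with one pass, 0.722 with pooled Grubbs, 0.728 with 5% Winsorizing either way.
- Log SD 1: repeated by-group Grubbs removes about 19 per group. d goes from 0.74 to 1.09, specificity from 0.736 to 0.770, sensitivity from 0.733 to 0.717. Pooled Grubbs lowers specificity to 0.721.
- Only 30% of cases elevated: repeated pooled Grubbs removes about 133 cases, and d falls from 0.73 to 0.13.
- Unequal spread: by-group 5% Winsorizing moves specificity either way (0.873 to 0.969, or 0.507 to 0.434), while pooled Winsorizing leaves it unchanged.

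Winsorizing usually leaves specificity alone because capping values that lie beyond the cut-off reclassifies nobody.

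**The case against.** The strongest reply is that most of the premises are supplied by the reviewer. The protocol does not say the marker is skewed, that flagged values are deleted, or that the rule applies to the marker. Alpha, passes, percentiles and pooled or by-group use are details that a statistical analysis plan may hold, and their absence is no finding. If the marker is normal, Grubbs removes almost nothing; if it is not, the test becomes "Mann-Whitney U tests (non-normal data"), which is robust. All of this stands and sets the size of the point. It does not remove it: a normal-theory test is named for data the same section expects may be non-normal, the trigger is purely statistical, and d and the accuracy measures are reported whichever test is chosen.

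A reader might infer that the plan inflates specificity by discarding its false positives. The documents do not support that as a general statement. It needs deletion among controls. By-group Grubbs also discards true positives, so the Youden index barely moves (0.734 + 0.736 − 1 = 0.470 against 0.729 + 0.745 − 1 = 0.474). A larger effect appears at a fixed cut-off with a true false-positive rate of 5.0%, where the reported rate becomes 4.0% at log SD 0.5. That is not the planned cut-off.

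It is also fair to say that raw-scale d is a poor summary of skewed data. On the log scale d is 1.20 by construction in these scenarios, above the 1.15 after Grubbs, so keeping all values need not give a smaller standardized effect.

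**Conclusion.** The point holds in a limited form. The stated outlier rule does not fit the plan's own allowance for non-normal levels, and it lets a valid marker value be altered for being extreme rather than for being faulty.

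The firmest consequence is for raw-scale Cohen's d, which usually rises: by about 0.10 (repeated by-group Grubbs) to 0.18 (5% by-group Winsorizing) at log SD 0.5, and by about 0.12 under by-group Winsorizing of normal data. The effect on sensitivity and specificity at the Youden cut-off is modest at log SD 0.5 to 0.8, about 0.01 to 0.02, and its direction depends on how the rule is applied.

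These sizes rest on assumed distributions and assumed ways of applying the rule, and on its being applied to the marker at all. Severity: minor to moderate.

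**What to change.** Replace the outlier phrase in section 5.3 with three statements:

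1. A marker value is excluded or re-measured only for a documented assay failure, judged without knowledge of group, and every such value is listed with its reason.
2. All valid values enter the main analysis. If the marker is skewed, rank methods or a prespecified log scale are used, and Cohen's d is reported on the scale of that analysis.
3. Any Grubbs-trimmed or Winsorized result is a labelled sensitivity analysis, with the variable, threshold, number of passes and by-group or pooled use fixed beforehand.

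The cost is wording only. Raw-scale d, and specificity if controls would otherwise have been deleted, may look slightly less favourable.

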Succinylation modification, as a widely existing post-translational modification of proteins, has potential biomarker value in malignant solid tumors. Besides tumors, existing studies have shown that some diseases (such as inflammatory diseases, infectious diseases, metabolic diseases, cardiovascular diseases, neuro-psychological diseases, etc.) have certain correlations with non-histone succinylation modification. The role of histone succinylation modification in other diseases is currently lacking in relevant clinical research evidence and awaits further exploration in this study. Therefore, this research focuses on malignant solid tumors, not only filling the knowledge gap in this field but also laying the foundation for future expansion to other diseases.

2.1.2 project objective

The core objective of the project is to systematically verify and establish the clinical

application value of serum histone succinylation modification as a novel, efficient and non-invasive pan-tumor biomarker.

Objective 1: Verify the potential of pan-tumor screening: Through large-scale case-control studies, it is clearly confirmed that there are significant differences in histone succinylation levels in serum between patients with malignant solid tumors and healthy individuals, thereby providing a solid evidence-based basis for developing it into a blood-based early screening tool suitable for multiple tumor types.

Objective 2: Exploring clinical application scenarios: The project will conduct an in-depth analysis of the association between serum histone succinylation levels and different types of tumors as well as different tumor stages, and evaluate its ability to distinguish tumor types and reflect disease progression. Meanwhile, analyze its correlation with therapeutic effects (changes in levels before and after surgery, radiotherapy, and systemic treatment) and clinicopathological characteristics, and explore its application prospects in dynamic monitoring of therapeutic effects and prognosis assessment.

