2.2 Risk/Benefit assessment

risk assessment:

This study was an observational one, and the core intervention was only a single venous blood sample collection of 3mL (approximately 1ml of serum). This operation

is a routine and mature medical practice in clinical practice, with extremely low and controllable risks.

Benefit evaluation:

Cancer patients: They will not receive immediate individualized diagnosis or treatment recommendations from this study. However, the data it contributes will drive the development of better tumor markers, which may benefit its future disease management (such as more precise follow-up monitoring).

Healthy control subjects: Contribute to establishing baseline standard values for healthy populations and promote public health. After the research is completed and the method is mature, the baseline data in which it participated may provide a reference background for its own future similar screening.

三、 Research objectives and endpoints

3.1 objective

3.1.1 main purpose

To evaluate the differences in serum histone succinylation between malignant solid tumors and healthy individuals, in order to verify its early screening value.

3.1.2 secondary objective

To clarify the correlation between histone succinylation modification in serum and different types of tumors and tumor stages, and to statistically analyze the correlation between histone succinylation in serum and therapeutic effects (including surgical treatment, radiotherapy, and systemic therapy) as well as clinicopathology.

3.2 evaluation index

The evaluation indicators are: the sensitivity, specificity, positive predictive value, negative predictive value of the serum histone succinylation screening method, and the predictive value of the Youden index (early diagnosis, therapeutic effect evaluation and prognosis).

四、 study population

4.1 inclusion criteria

case group

- 1) ≥ 18 years old, gender not limited;
- 2) Malignant solid tumors diagnosed by cytology or histology require subsequent anti-tumor treatment (systemic therapy, radical or concurrent chemoradiotherapy/radiotherapy, or surgical treatment).

control group

- 1) ≥ 18 years old, gender not limited;
- 2) Non-tumor patients undergoing health check-ups;

4.2 exclusion criteria

- 1) Pregnant women
- 2) Those with severe mental disorders or language communication disorders;
- 3) Other circumstances where the researcher deems it unsuitable to participate in this study.

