5.2 Research design process

5.2.1 Study the specific implementation process

1. Phase One: Screening and enrolling the population

- i. Conduct ethical reviews and clinical research protocol reviews for the project;
- ii. It is planned to select 500 patients with malignant solid tumors, collect their basic information and sign the "Informed Consent Form".
- iii: It is planned to select 500 healthy subjects and collect basic information.

2. Phase Two: Collect blood samples for serum histone succinylation detection

[figure not shown]
Blood samples were collected from all 500 enrolled individuals and 500 healthy subjects who met the requirements for serum histone succinylation detection.

3. Phase Three: Statistical analysis of Screening Results

- i. Western blot was used to evaluate the differences in serum histone succinylation between malignant solid tumors and healthy individuals to verify its early screening value.

ii. Statistically analyze the correlation between serum histone succinylation and tumor efficacy (including surgical treatment, radiotherapy, and systemic therapy) as well as clinicopathology. The therapeutic effect was evaluated using RECIST1.1 criteria.

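### The main purpose is early screening value, yet accuracy is planned with all stages pooled and the only stage restriction removes stage I

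*Protocol*

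**What the plan says.** **Purpose.** Section 3.1.1 sets the main purpose as a comparison of serum histone succinylation between cancer patients and healthy people "in order to verify its early screening value". Section 5.2.1 (Phase Three) repeats this, and Objective 1 in section 2.1.2 looks towards a "blood-based early screening tool suitable for multiple tumor types". Section 3.2 lists sensitivity, specificity and the predictive values, and ends with "the predictive value of the Youden index (early diagnosis, therapeutic effect evaluation and prognosis").

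**Population.** The case criterion in section 4.1 begins "Malignant solid tumors diagnosed by cytology or histology require subsequent anti-tumor treatment" and sets no stage limit. Controls are people without tumours attending health check-ups. Section 5.3 plans 500 in each group, with no quota by stage.

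**Accuracy analysis.** Section 5.3 plans an AUC with a bootstrap interval, a cut-off that maximises the Youden index, and sensitivity, specificity, PPV and NPV with exact intervals. None of these is restricted or broken down by stage.

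**Where stage enters section 5.3.** There are three places:
- Cuzick's "trend test was used to analyze the ordered association of TNM stages";
- stage as an adjustment variable in the Cox model;
- the sensitivity analysis: "Robustness was verified by excluding stage I tumors".

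**The concern.** A case-control comparison across all stages shows whether people with diagnosed cancer differ from check-up attendees. The claim about early screening goes further, because it depends on how well the marker separates early-stage cases from controls. The plan prespecifies one stage-restricted check, and that check discards stage I.

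The direction matters too. If the marker rises with stage, which the protocol tests but does not assume, dropping stage I must raise AUC and sensitivity. Under the label of robustness, a higher figure looks like support. For the stated purpose it is indirect evidence that stage I performs worse. A good pooled AUC and a better AUC without stage I could then be cited for early detection with stage I and I-II accuracy never shown.

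**Working it through.** **1. Does any planned analysis give early-stage accuracy?**

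| Analysis in section 5.3 | What it estimates | Early-stage AUC or sensitivity? |
|---|---|---|
| ROC, Youden cut-off, sensitivity, specificity, PPV, NPV | Accuracy, all stages together | No |
| Cuzick's trend test | Order of marker levels over TNM stage among cases | No |
| Cox model with stage as covariate | Prognosis | No |
| 70%-30% split | Cut-off training and validation, not by stage | No |
| Exclusion of stage I | Result in the remaining stages | No; stage I is removed |

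**2. How large could the gap be?** The protocol gives no stage mix and no gradient, so everything below is an illustration under assumptions.

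Model: controls N(0,1); cases in stage k N(d_k,1); stage shares w_k = 20/25/25/30% for stages I-IV.
- Stage AUC = Φ(d_k/√2). A pooled AUC is the share-weighted mean of the stage AUCs.
- Cut-off c maximises pooled sensitivity plus specificity. It is held fixed for every row of the table further down.
- Sensitivity in stage k = 1 − Φ(c − d_k); false-positive rate = 1 − Φ(c).

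Base gradient d = 0.4/0.9/1.3/1.8:
- Stage AUCs: 0.611, 0.738, 0.821, 0.899.
- Pooled: 0.20×0.611 + 0.25×0.738 + 0.25×0.821 + 0.30×0.899 = 0.78 (unrounded 0.7815).
- Excluding stage I: (0.25×0.738 + 0.25×0.821 + 0.30×0.899)/0.80 = 0.82 (unrounded 0.8240).
- Stages I-II: (0.20×0.611 + 0.25×0.738)/0.45 = 0.68.
- Cut-off 0.669, false positives 25%. Stage I sensitivity: 1 − Φ(0.669 − 0.4) = 0.394.

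Sensitivity at the pooled cut-off:

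| Assumed gradient (d, stages I-IV) | Cut-off; false positives | Pooled | Excluding I | Stage I | Stages I-II |
|---|---|---|---|---|---|
| Shallow 0.8/1.0/1.2/1.4 | 0.580; 28% | 70% | 73% | 59% | 63% |
| Base 0.4/0.9/1.3/1.8 | 0.669; 25% | 67% | 74% | 39% | 50% |
| Steep 0.2/0.8/1.4/2.0 | 0.742; 23% | 64% | 73% | 29% | 42% |
| None, d = 1.2 throughout | 0.600; 27% | 73% | 73% | 73% | 73% |

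The excluding-stage-I column is 73-74% in every row, while stage I sensitivity runs from 29% to 73%. The planned check therefore carries almost no information about stage I when read alone.

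**3. Can a reader recover stage I from the planned figures?** For AUC, in part. With a stage I share of 20%:
- unrounded: (0.7815 − 0.8×0.8240)/0.2 = 0.611;
- from reported values of 0.78 and 0.82, the bounds are (0.775 − 0.8×0.825)/0.2 = 0.575 and (0.785 − 0.8×0.815)/0.2 = 0.665.

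That is a range of 0.09 from rounding alone, with no confidence interval and no stage I sensitivity beside it unless the reader derives them.

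**The case against.** **The analysis plan is not at hand, and accuracy by subgroup is often left to it.** That is true, and a missing subgroup table alone would not be a finding. But the protocol does fix a stage-based check, aims it away from early disease and labels it robustness. Objective 2 and section 3.1.2 commit to studying marker levels by stage, which does not supply accuracy.

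**The sentence does not say which analysis is rerun without stage I.** This stands. Its place beside the cut-off validation makes accuracy the natural reading. If it concerns only mean levels or the Cox model, the misleading rise in AUC would not appear, but the plan would then have no stage-based check of accuracy at all.

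**Pooled and restricted results side by side, with a trend test, would themselves hint at weaker stage I performance.** They would. The defect is indirect reporting rather than concealment, and the back-calculation above shows how imprecise that indirect route is.

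**The stage mix is assumed.** With an assumed mix of 5/15/30/50% and the base gradient, AUC is 0.84 pooled and 0.85 without stage I, so the rise nearly disappears. Stage I AUC is still 0.61, so a small rise does not rule out poor early-stage accuracy. Re-optimising the cut-off after the exclusion changes the base-case sensitivity only from 74% to 73%.

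**The stated aim can be read more modestly, as a case-control difference that leads to later development.** The main analyses do answer that question. The early-screening wording is nevertheless the protocol's own, and it appears in sections 2.1.2, 3.1.1 and 5.2.1.

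**Conclusion.** The concern holds and should be fixed. The main analyses validly test whether diagnosed cancer differs from check-up controls. They do not directly support a statement about early screening value, and the one stage restriction in the plan excludes the cases that would.

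The mismatch between purpose and analysis rests on the text alone. Its size is illustrative: under the assumed 20/25/25/30% mix, stage I sensitivity falls below the pooled figure by 11 to 12 points with a shallow gradient, about 28 with the base gradient and about 35 with a steep one. It is zero if the marker differs equally in all stages. The protocol does not define early by stage; taking it as stage I or I-II is an assumption made here, and early-stage accuracy goes unreported on either reading.

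**What to change.** Replace or supplement the exclusion of stage I in section 5.3 with wording such as:

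> AUC (bootstrap 95% CI), and sensitivity at the overall cut-off (Clopper-Pearson 95% CI), will be reported against all controls for stage I, stages I-II, stage III and stage IV. Any statement on early screening or early diagnosis will rest on the stage I and I-II results.

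If the exclusion analysis is kept, name the analysis it reruns and do not describe it as verifying early screening value. State that the pooled AUC supports only discrimination of diagnosed cancer from check-up controls.

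**Cost.** Only the analysis wording changes, because TNM stage is already needed for the trend test and the Cox model. The price is precision, and with no stage quota the stage I count is unknown. Exact 95% intervals for assumed counts:

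| Cases detected | Interval | Half-width |
|---|---|---|
| Stage I, 39/100 | 29-49% | about 10 points |
| Stage I, 19/50 | 25-53% | about 14 points |
| Stage I, 10/25 | 21-61% | about 20 points |
| Stages I-II, 113/225 | 44-57% | about 7 points |

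Two limits remain. A stage I result pooled over tumour types reflects which types present early. A cut-off tuned on the same data flatters sensitivity, so the stage results are best also shown in the 30% validation part, where intervals will be wider still.
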